Study personnel will review the instructions printed on the package insert with subjects prior to dispensing the study medication. New study medication will be dispensed according to the Schedule of Assessments. The subject will be instructed to return the study medication packaging, including any unused medication, to the study site at each visit for assessment of compliance. Subjects will be asked whether they have taken their medication as instructed at each study visit. Any problems with compliance will be reviewed with the subject.

Compliance will be assessed in two ways. Subjects will be responsible for returning unused study drug to the site. Pills will be counted to determine compliance. Subjects will also be responsible for recording the date and time they take the study drug in a medication diary. Compliance is defined as taking between 75%-125% of dispensed study medication.

Dupilumab injections will also be recorded in the medication diary.

Withdrawal/Termination criteria:

The following are considered sufficient reasons for discontinuing a subject from study drug:

- Adverse events that the investigator believes may cause severe or permanent harm or which rule out continuation of study drug
- Lack of therapeutic effect:
 - Subjects who experience a significant flare of atopic dermatitis, as defined by a sudden intensification of eczema, or as a diagnosis of erythrodermic atopic dermatitis may be discontinued from treatment and enter the observational follow- up phase of the study.
 - In addition, if the subject, in his or her opinion, feels that their disease is worsening or not responding to treatment, they may withdraw consent to participate.
- Subject withdraws consent
- Subject lost to follow-up
- Death
- Protocol violation

The reason for discontinuation will be recorded in the subject's medical records.

D. Risk/benefit assessment:

- 1. **Physical risk**: Physical risk includes potential side effects or unknown adverse events related to study medication. It is unknown how the combination of apremilast with dupilumab will affect subjects. Side effects may be worse or intensified on this combination. Subjects may be at a slightly higher risk of infection than those taking the drugs individually, but this is unknown. It is unknown if this combination will improve atopic dermatitis. AD could stay the same or get worse.

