1. **Study Procedures**: At the initial visit, a Investigator's Global Assessment (IGA) of disease will be performed to determine if the patient meets the inclusion criteria. A score on the NRS Pruritus

scale will be determined. A thorough medical history and a review of prior/concomitant medications will be taken at the screening visit. A complete physical examination including weight and vital signs (temperature, blood pressure) will also be performed. At the following visits according to the Schedule of Assessments, a IGA, BSA, DLQI survey, vital signs, NRS pruritus scale, EASI, a complete or targeted physical exam and review of concomitant medications and adverse events will be performed. Additionally, drug dispensing and accountability will also occur at all visits after the screening visit according to the Schedule of Assessments.

- Lab monitoring is not standard of care for patients using apremilast in clinic settings for the treatment of psoriatic disorders. Patients with psoriasis are frequently prescribed apremilast in addition to psoriasis biologic injectables, and it is not standard of care to perform lab tests for these patients that is outside of what is recommended for monitoring the safety of their injectable biologic alone. Atopic dermatitis patients taking apremilast are not at any increased risk compared to psoriasis patients taking apremilast. Dupilumab is a biologic, but this specific biologic does not require lab monitoring. For these reasons, lab monitoring will not be performed during this study as it would cause research subjects to undergo unnecessary testing. However, for all patients taking apremilast, it is standard of care to monitor weight at treatment visits and to ask patients about adverse symptoms. Both of these will be performed during the study based on the schedule of assessments.
- 2. **Subject Timeline**: 24 week duration of study treatment.

F. Assessment of Subject Safety and Development of a Data and Safety Monitoring Plan

- AE data will be collected at each study visit by asking the subject about their symptoms. The PI will review all AE data as they are collected, and the PI will sign off on AEs during the study visit. The AEs for the subjects will be stored in the subject's study documents and updated at each study visit. AEs will be collected from the time of ICF signature through the end of the study at all study visits.

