	Basenne	± 3 days	3 days	± 3 days	10 ± 3 days	24 ± 3 days	nation
Informed Consent	Х	uujs		duyb	auyo	duyb	
Atopic Dermatitis diagnosis, medical history	Х						
Concomitant/prio r Medications	Х	Х	X	X	X	X	Х
Complete physical examination ²	Х						Х
Targeted physical examination ³		Х	Х	Х	X	Х	
Vital signs (Temperature, resting pulse, seated blood pressure)	Х	x	X	Х	Х	Х	Х
Demographic information ⁴	Х						
CLINICAL EVALUATION							
Assessment of atopic dermatitis ⁵	Х						
Investigator's Global Assessment of disease (IGA)	Х	X	Х	Х	Х	Х	Х
Body Surface Areas (BSA)	Х	Х	X	X	X	X	Х
NRS Pruritus scale	Х	Х	Х	Х	Х	X	Х
Eczema Area and Severity Index (EASI)	Х	Х	Х	Х	Х	Х	Х
Photography	Х	Х	Х	Х	Х	Х	Х
PATIENT REPORTED OUTCOMES							
Dermatology Life Quality Index (DLQI)	Х	X	Х	Х	X	Х	Х
OTHER ACTIVITIES							
Study Drug Dispensing	Х		X	X	X		
Drug Accountability		Х	X	X	Х	X	Х
Adverse Event Reporting		Х	X	X	X	X	Х
Review concomitant medications	Х	X	Х	Х	X	Х	Х
Urine pregnancy test ⁶	Х	X	Х	Х	Х		

¹Baseline visits may occur at the same time as the screening visit, or within 4 weeks of the screening visit.

²Complete physical examination includes weight, general appearance, skin, HEENT (head, eyes, ears, nose, throat), heart, lungs, abdomen, lower extremities, neurologic and lymph nodes. Height will be recorded at screening only.

³ Targeted physical examination consists of weight, examination of heart, lungs, abdomen, lymph nodes, and lower extremities, as well as any area of patient-reported AEs.

⁴ Demographic information including but not limited to age, race, gender, ethnicity

⁵ For study eligibility, subjects must have active atopic dermatitis at Screening, which has been diagnosed or confirmed by a dermatologist.

⁶ Urine pregnancy test (human chorionic gonadotropin; HCG) is required only for women of child-bearing potential

Assessments of Efficacy:

- Investigators Global Assessment (IGA)
- **Body surface area** (BSA) of involved skin will be measured at Screening, Baseline, and at following visits according to the Schedule of Assessments until study completion.
- Numerical Rating Scale (NRS) Pruritus Scale
- EASI
- DLQI

Assessments of Health-Related Quality of Life:

- Dermatology Life Quality Index will be assessed by the subject at Day 1, and Weeks 2, 4 8,

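### Does a compliance range of 75% to 125% of drug dispensed, with no interval named, need to be redefined?

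*Protocol*

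**What the plan says.** The Treatment Compliance section of the Protocol gives the rule: "Compliance is defined as taking between 75%-125% of dispensed study medication". It describes two sources. The first is the tablet count: "Pills will be counted to determine compliance". Patients bring back packaging, "including any unused medication, to the study site at each visit for assessment of compliance". The second is the patient's own record, through "recording the date and time they take the study drug in a medication diary". Patients are also asked at every visit whether they took the drug as instructed, and the section adds: "Any problems with compliance will be reviewed with the subject".

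The section does not say whether the percentage applies per visit, per dispensing interval or over the whole study. It also does not say which source prevails if count and diary differ.

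Study Procedures says that "drug dispensing and accountability will also occur at all visits after the screening visit according to the Schedule of Assessments", so it defers to the Schedule. There, the row "Study Drug Dispensing" is marked at Visit 1 and Weeks 4, 8 and 16. The row "Drug Accountability" is marked at Weeks 2, 4, 8, 16 and 24 and at early termination. Week 2 therefore has a count but no new supply. The SAP does not mention compliance.

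**The concern.** Two features look wrong. First, an upper limit of 125% makes sense against doses scheduled, but the stated denominator is drug dispensed. Nobody can take more than they were given, so the part of the range from 100% to 125% is empty for a tablet count.

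Second, drug is counted at Week 2, in the middle of the first supply. A literal reader who divides tablets taken by tablets dispensed at that visit would score a perfectly adherent patient at about half, well below 75%. The same reading would put a patient taking twice the scheduled tablets near 100%.

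If the range decided who enters an analysis or who is withdrawn, this would misclassify patients in a trial that aims for only 16 completers.

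**Working it through.** The range is a definition with no derivation, so there is no plan figure to reproduce. The check asks what the ratio reads under each interval, and what depends on it.

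**Inputs.**
- Dosage Regimen: one dose on Day 1, two a day from Day 2, so doses due to Day n = 2n − 1.
- Schedule of Assessments: dispensing and counting visits as above, with visit windows of ±3 days.
- Assumptions, because quantities are not stated: one tablet per dose, and each supply lasts to the next dispensing visit. Six spare tablets (three days) serve as a variant.

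Doses due: Day 14, 27; Day 28, 55; Day 56, 111; Day 112, 223; Day 168, 335.

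**1. Upper limit.** Taken = dispensed − returned, and returned cannot be negative, so taken/dispensed ≤ 100%. The one exception is scoring carried-over tablets against the new supply alone. With 14 left from 55, (56 + 14)/56 = 125%. That patient took 41/55 = 74.5% in the interval before, and no such carry-over rule is described.

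**2. Ratio applied at Week 2.**
- Full adherence: 27/55 = 49.1%.
- Lowest (Day 11, supply to Day 31): 21/61 = 34.4%.
- Highest (Day 17, supply to Day 25): 33/49 = 67.3%.
- Tablets needed to pass: 0.75 × 55 = 41.25, so 42, and 42/27 = 156% of those due.
- Double the scheduled tablets: 54/55 = 98.2%.

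**3. Ratio applied per dispensing interval or over the study, full adherence.**

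| Interval | Exact supply | Six spare |
|---|---|---|
| Visit 1 to Week 4 | 55/55 = 100% | 55/61 = 90.2% |
| Week 4 to 8 | 56/56 = 100% | 56/62 = 90.3% |
| Week 8 to 16 | 112/112 = 100% | 112/118 = 94.9% |
| Week 16 to 24 | 112/112 = 100% | 112/118 = 94.9% |
| Whole study | 335/335 = 100% | 335/359 = 93.3% |

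The Week 2 problem disappears. Spare tablets do raise the effective lower limit: 0.75 × 61 = 45.75, so 46 tablets, and 46/55 = 83.6% of doses due in the first interval.

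**4. What a scheduled-dose denominator would gain.**
- Week 2: full adherence reads 27/27 = 100%. The range becomes 20.25 to 33.75 tablets, so 34 or more would be caught.
- Week 4 ceiling: 55/55 = 100%, or 61/55 = 111% with six spare. Exceeding 125% needs more than 1.25 × 55 = 68.75, so at least 69 tablets dispensed.
- Week 16 ceiling: 223/223 = 100%, or (223 + 18)/223 = 108%.
- Week 24 ceiling: 335/335 = 100%, or (335 + 24)/335 = 107%.

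The upper limit would work at Week 2 and stay out of reach at these later counts.

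**5. Where the range is used.** The efficacy set is defined by completing at least 16 weeks of treatment (Protocol, Statistical methods; SAP). The safety set is defined by one dose. No endpoint or planned tabulation refers to compliance. The Withdrawal/Termination criteria list protocol violation in general terms and do not cite the range.

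**The case for a change.** The strongest argument for a change is that the denominator is wrong on its face and one sentence would correct it. The empty upper band needs no assumption about supply. The interval really is missing. A per-interval reading also does not rescue every count: accountability is done at early termination, and a fully adherent patient stopping at Week 12 would read 56/112 = 50% of the Week 8 supply, or 167/223 = 74.9% cumulatively. Both are below 75%.

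The arithmetic stands, but the consequences do not follow. A patient stopping at Week 12 is outside the efficacy set because of the completion rule, whatever the ratio says. The Protocol does not tie the review of compliance problems to the percentage: that sentence follows the question about taking drug as instructed, comes before the definition, and covers any problem. A patient taking double would return one tablet of 55 with two weeks still to run. The count itself, the dated diary and the visit question would all show it, and a diary tally is not capped at 100%.

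The one-sentence remedy is also incomplete. As step 4 shows, the 125% limit would stay beyond a pill count at the end of each supply period unless far more tablets were dispensed than the schedule needs.

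**Conclusion.** No change to the plan is needed. Two narrow observations hold: the upper limit is inert by pill count, and the interval is unnamed. The Week 2 misreading (49%, range 34% to 67%) arises only if the ratio is scored mid-supply against everything dispensed, which the Protocol does not require. It also rests on an assumed supply lasting to Week 4 at one tablet per dose. An analyst describing adherence would naturally score completed supply periods or the whole study, and would read over-use from the diary or early run-out. Full adherence then reads 90% to 100% under the supplies considered.

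The range feeds no endpoint, analysis set, planned summary or stated discontinuation rule, so redefining it would change no result or conclusion. It would affect only how adherence is described, and would leave most of the upper-limit defect in place.

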 - v. Mean and percentage change from baseline in Eczema Area and Severity Index (EASI) score at week 16

Safety Endpoints:

Safety and tolerability will be evaluated according to the frequency and severity of adverse events and changes in physical examinations or vital signs.

II. Research Plan

A. Overall Study Design:

Open label phase 2 investigational study of efficacy and safety of apremilast 30 mg BID in chronic atopic dermatitis when added to the FDA approved treatment dupilumab for atopic dermatitis that is not providing adequate clinical responses. The study will have 1 phase:

• Open label treatment period apremilast 30 mg BID

Following informed consent, subjects will be screened on the basis of atopic dermatitis severity and inadequate treatment response to current therapies. IGA, BSA, pruritus NRS, EASI, complete physical examination, medical history, and concomitant medications will be reviewed. Eligible subjects will be administered treatment with apremilast 30 mg BID while continuing their prior inadequate atopic dermatitis treatment regimen. During the treatment phase, study drug will be provided in an oral form and will be titrated over 5 days and then taken twice daily thereafter. Subjects return to clinic for reevaluation. Efficacy endpoints will be assessed at weeks 2, 4, 8, 16, and 24. Week 16 is the last week of study drug dispensation. Efficacy and safety indices will be assessed as per the Schedule of Assessments.

Treatment Assignment and Randomization

No randomization will be used, as this is an open label study. There will be no blinding and investigators will have knowledge of the treatment each subject is administered.

All patients seen in the Tufts Dermatology Clinic during the enrollment period who are not currently responding to existing FDA approved atopic dermatitis therapy and thus have not achieved a IGA of 0 or 1 at screening, and meet all other inclusion/exclusion criteria, will be offered participation in the study.

B. Statistical methods:

Sample size: We will screen up to 20 patients to ensure that 16 patients complete the study.

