Dosage Regimen: Apremilast will be administered to patients as 30 mg oral tablets taken twice daily for 24 weeks. An initial 5-day titration will be implemented to improve tolerability. The study drug will be started the morning of Day 1 at 10 mg. On Day 2, the study drug will be taken at 10 mg in both the morning and evening. On Day 3, the study drug, will be taken at 10 mg in the morning and 20 mg in the evening. On Day 4, the study drug will be taken at 20 mg in both the morning in evening. On Day 5, the study drug will be taken at 20 mg in the morning and 30 mg in the evening. On Day 6 and thereafter, the study drug will be taken at 30 mg in morning and evening. Doses should be 12 hours apart. Subjects will be instructed that apremilast can be taken with or without food and that the tablets should not be crushed, split, or chewed. Subjects will also be instructed to store tablets below 30°C (86°F). Subjects will simultaneously continue on their prior atopic dermatitis treatment regimens in addition to taking apremilast. If a subject misses a dose of the study drug, they may take it as soon as they remember, as long as it is more than 6 hours before the next scheduled dose. In this case, the subject will take the missed pill, and then take their next pill at their usual dosing time and resume their normal dosing schedule. If the subject forgets to take a dose and it is <6 hours before their next scheduled dose, they should not take the forgotten pill and should not double-dose. Subjects should take their next scheduled dose at their usual time and resume their normal dosing schedule. Subjects will be responsible for recording the dates and times that they dose, and mark any missed dose as "missed" in their dosing diary. Treatment compliance will be assessed as described on page 8 of the protocol.

Record of administration: Accurate recording of all study drug administration (including dispensing and dosing) will be made in the appropriate section of the subject's source documents.

Study Medication Accountability: The investigator or designee(s) is responsible for accounting for all study medication that is issued to and returned by the subject during the course of the study. If any study drug is lost or damaged, its disposition should be documented in the subject's source documents.

E. Specific methods and techniques used throughout the study:

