Reportable new information will be reported to the IRB per the Tufts Health Sciences IRB's Reportable New Information policy.

- Accountability procedures as they relate to drugs, devices, and data: The investigator or designee(s) is responsible for accounting for all study medication that is issued to and returned by the subject during the course of the study. If any study drug is lost or damaged, its disposition should be documented in the subject's source documents.
- The study drug will be stored in the investigational pharmacy. IDS will be responsible for dispensing medication. All unused drug will be returned to IDS at the end of the study. The research coordinator is responsible for communicating with IDS. The PI is responsible for signing all drug order forms.

Contraception Education

The risks to a fetus or to a nursing child from apremilast are not known at this time. Results of the animal and in vitro studies can be found in the IB.

All females of childbearing potential (FCBP) must use one of the approved contraceptive options as described in section II:C:6 while on investigational product and for at least 28 days after administration of the last dose of the investigational product.

When a female subject of childbearing potential's contraceptive measures or ability to become pregnant changes at the time of study entry or at any time during the study, the Investigator will educate the subject regarding options and correct and consistent use of effective contraceptive methods in order to successfully prevent pregnancy.

Pregnancies

Pregnancies and suspected pregnancies (including a positive pregnancy test regardless of age or disease state) of a female subject or the female partner of a male subject occurring while the subject is on study

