drug, or within 30 days of the subject's last dose of study drug, are considered immediately reportable events. Study drug is to be discontinued immediately and the subject instructed to return any unused portion of the study drug to the investigator(s). The pregnancy, suspected pregnancy, or positive pregnancy test must be reported to Amgen Safety immediately facsimile using the Pregnancy Report form provided by Amgen. An authorization form to request the collection of this information from the pregnant partner of a male subject will be submitted to the IRB for review and approval prior to the collection of this information. The study team will request that subject approach their pregnant partner to obtain authorization, and the pregnant partner may contact the study team for more information.

G. Subject Participation

- 1. **Recruitment**: Recruitment will occur through the outpatient dermatology clinic at Tufts Medical Center once IRB approval is obtained. Goals for recruitment in terms of screening treatment regimens include: 16 subjects completing the study. Up to 20 may be screened to allow for screen fails.
 - Dermatologists in the TMC department of dermatology will be informed about the ongoing trial and its key inclusion/exclusion criteria. Dermatologists can inform their patients about the study during the patient's regular scheduled clinic visit. If a patient is interested, research staff will come down to the dermatology clinic to inform the patient further. If the subject chooses to proceed with a screening visit, this will be conducted in a private research room where informed consent will be obtained. Alternatively, the screening visit can be scheduled for a future date. Dermatologists may also tell their patients about this study and provide research staff contact information to the patient
 - The clinical recruitment website will provide online information about the study. Additionally, this trial will be listed on clinicaltrials.gov. Study team contact information will be provided in both of these websites, and interested subjects may call the department for more information. There are no other recruitment materials.
 - These two methods have been effective in the past for our recruitment of other investigator-initiated trials of similar sample sizes.
- 2. Registration: Not applicable.

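### No pregnancy test closes the last eight weeks of apremilast, and no contact covers the 30 days afterwards in which a pregnancy must be reported

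*Protocol*

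**What the plan says.** **Length of treatment.** Protocol, Dosage Regimen: "Apremilast will be administered to patients as 30 mg oral tablets taken twice daily for 24 weeks". Drug is last dispensed at Week 16, for the eight weeks that follow.

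**Duties after the last dose.** Contraception Education requires women of childbearing potential to use contraception "for at least 28 days after administration of the last dose of the investigational product", and inclusion criterion 7 sets the same 28 days for men. The reason given is "The risks to a fetus or to a nursing child from apremilast are not known at this time". Under Pregnancies, a pregnancy or suspected pregnancy in a subject or a male subject's partner, while on drug or within 30 days of the "last dose of study drug, are considered immediately reportable events". The same section adds "Study drug is to be discontinued immediately".

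**Testing and contact.** The pregnancy-test row of the Schedule of Assessments has five marks: Visit 1 and Weeks 2, 4, 8 and 16. The Week 24 and Early Termination cells are blank. Footnote 6 limits who is tested, not when: "Urine pregnancy test (human chorionic gonadotropin; HCG) is required only for women of child-bearing potential". The Schedule has no column after Week 24 other than Early Termination. Section F collects adverse events at study visits, by asking about symptoms.

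**Follow-up phase.** The Withdrawal/Termination criteria let a subject who stops for a significant flare "enter the observational follow- up phase of the study". Overall Study Design says "The study will have 1 phase", namely open-label treatment.

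**The concern.** The Protocol treats pregnancy during and shortly after exposure as serious enough for immediate reporting, and says that fetal risk is unknown. Its visit plan gives the site little means of learning of such a pregnancy late in treatment or after it. The last stretch of dosing is as long as any other and is the only one that no test closes. After the last visit nothing prompts a subject to say anything.

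The flare wording adds to the uncertainty. A reader could take the named follow-up phase to be where post-treatment safety is handled, but that phase has no stated content.

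At stake is whether pregnancies exposed to apremilast plus dupilumab are found and reported. The Week 16 response rate and the other efficacy summaries are not involved.

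**Working it through.** The plan gives no figure for this, so the check is a reading of the Schedule plus calendar arithmetic.

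**Inputs.** Tests at Weeks 0, 2, 4, 8 and 16, with a window of ±3 days from Week 2 on (Schedule of Assessments). Last dose taken to be at the Week 24 visit, ±3 days (Dosage Regimen; Schedule). Reportable period runs to 30 days after the last dose (Pregnancies).

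**1. Is each dosing interval closed by a test?**

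| Interval | Days | Test at its end |
|---|---|---|
| Week 0 to 2 | 14 | yes |
| Week 2 to 4 | 14 | yes |
| Week 4 to 8 | 28 | yes |
| Week 8 to 16 | 56 | yes |
| Week 16 to 24 | 56 | no |

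With both visit windows the last interval is 56 − 6 = 50 to 56 + 6 = 62 days.

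**2. Subject who completes treatment.** The last test is on Day 16 × 7 = 112, the last dose on Day 24 × 7 = 168, and the reportable period ends on Day 168 + 30 = 198. From last test to end of period is 198 − 112 = 86 days (80 to 92 with windows): 56 on drug and 30 off drug. The 30 days off drug have no scheduled test or contact.

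**3. Subject who stops early.** There is no test at Early Termination, so the time from last test to end of the reportable period is the time since that test plus 30 days. The minimum is 30 days, when drug is stopped on a test day. The maximum, with both windows, depends on when drug is stopped:

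- before Week 4: 14 + 6 + 30 = 50 days
- Weeks 4 to 8: 28 + 6 + 30 = 64 days
- Weeks 8 to 24: 56 + 6 + 30 = 92 days

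**4. Is there an unlisted follow-up visit?** The payment terms are $50 per visit up to $300. That is 300 / 50 = 6 visits, which matches Visits 1 to 6 and leaves none for follow-up.

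**5. After the change proposed below.** For a completer the last test moves from Day 112 to Day 168. The interval on drug not closed by a test falls from 56 days to 0, and the time from last test to end of period falls from 86 to 30 days. One telephone contact then falls at about Day 198, where now there is none.

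**The case against.** **The remedy does not protect the fetus.** A reader might infer that the missing tests prolong exposure, because the Pregnancies section requires drug to be stopped. The Schedule does not support that. Week 24 is the end of dosing, and Early Termination and a later call also come at or after stopping. A pregnancy that begins just after Week 16 is exposed for the same time with or without the new tests. This stands: the gain is in detection and reporting only.

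**The 86 days overstate the gap.** A reader might also infer that 86 of 198 days (43%) go unmonitored. Of those 86, 56 equal the Week 8 to 16 interval, which nobody disputes. Week 24 and Early Termination also include adverse event questioning, a physical examination and a medication review, so a pregnancy that the subject already knows of may well come out there. This stands too. The true gaps are the missing test at the end of dosing and the 30 days with no prompt.

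**Tests may be tied to dispensing.** Visit 1 and Weeks 4, 8 and 16 have both; Week 24 has neither. That is a coherent rule, but it does not account for Week 2, which has a test and no dispensing.

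**A duty to report is not a duty to test.** This is correct. The Protocol promises no testing through Day 30, so it breaks no rule of its own. Nor is a planned safety summary shown to change: the safety endpoint is adverse events, examinations and vital signs, and pregnancy is handled separately.

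**Instructions may exist elsewhere.** The consent form and part of the subject participation section (between items 7 and 11) were not available. They may tell subjects what to report after the last dose. The Schedule, where tests and visits belong, is present and shows none.

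**Conclusion.** The point holds as a cheap improvement of minor severity. The last 56 days of dosing (50 to 62) end with no pregnancy test, Early Termination has none, and the 30-day reportable period after the last dose has no scheduled contact. A pregnancy not yet recognised at the last visit, or starting after it, would reach the site only through the subject's own report.

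This rests on the last dose falling at about Week 24, on the two blank cells in the Schedule being intended, and on the unavailable text adding no visit. The number of women of childbearing potential is not given. At most 20 subjects are screened, and contraception is mandatory, so the expected number of cases is small.

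The undefined follow-up phase is a minor wording conflict. A reader might infer that outcomes after a flare are lost. The documents do not support that, since Section F has adverse events recorded with onset, resolution and severity, and the Early Termination visit repeats the skin assessments.

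**What to change.** 1. Schedule of Assessments: mark the urine pregnancy test at Week 24 and at Early Termination for women of childbearing potential.
2. Schedule of Assessments: add one telephone contact about 30 days after the last dose for every treated subject, asking about pregnancy (including a partner's pregnancy) and adverse events.
3. Withdrawal/Termination criteria: replace the reference to a follow-up phase with completion of the Early Termination visit.

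**Cost.** One urine test per woman of childbearing potential at a visit that already exists, at most 20 telephone calls, and an IRB-approved amendment with a revised consent form and reconsent of current subjects. A telephone contact leaves the six paid visits as they are. No efficacy assessment or stopping criterion changes.
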